7.6 Analysis of Safety Endpoints

Safety data will be summarized descriptively. No inferential statistics will be provided. All safety analyses and summaries will be based on the safety population.

7.6.1 Adverse Events

Adverse events (AEs) will be coded using the World Health Organization Drug Dictionary (WHO-DDE), version as defined in the DMP.

Incidence for the following treatment-emergent adverse events will be summarized by system organ class, preferred term and treatment based on the safety analysis set. Subjects are counted only once within each system organ class and each preferred term.

- All TEAEs
- All TEAEs by fostamatinib dose at onset
- All TEAEs by maximum severity in the following order: severe, moderate and mild (if severity is missing, the AE will be considered as severe for summary tables and will be presented in the data listing with a missing severity)

- All TEAEs by strongest relationship to study drug in the following order: probable, possible and unlikely (the relationship to study drug will be determined by investigators). If causality is missing, the adverse event will be considered probable for summary tables but will be presented in the data listing with a missing relationship.
- Serious TEAEs
- Serious TEAEs by fostamatinib dose at onset
- TEAEs leading to discontinuation of study treatment
- TEAEs leading to discontinuation of study treatment by fostamatinib dose at onset
- TEAEs of special interest (AESI) (including—but not limited to—increases in ALT, AST, and/or total bilirubin, absolute neutrophil counts (ANC) < 1000/mm³ or 1.0 x 10⁹/L, severe diarrhea, hypertension uncontrolled by oral antihypertensive medications that recorded in dose adjustment)
- TEAEs of special interest by fostamatinib dose at onset

All AEs, serious AEs, deaths, AEs leading to discontinuation of study drug, and AEs of special interest will be listed in by-subject listings separately.

7.6.2 Clinical Laboratory Evaluations

Actual values and the change from baseline to each scheduled visit in hematology, serum chemistry, and quantitative urinalysis test results will be summarized by dose. Actual values of categorical urinalysis test results will be summarized by dose and scheduled visit.

Shift tables will be used to summarize laboratory tests. Normal ranges for each parameter in hematology and serum chemistry will be used to categorize the test results as low (value lower than the lower limit of normal [LLN]), normal (value within the normal range), or high (value higher than the upper limit of normal [ULN]).

Additionally, number and percentage of subjects with elevated transaminase tests or who meet Hy's law criteria during the post-baseline (defined as the assessments after the first dose of study drug) will be summarized by study stage. All test results for AST, ALT, total bilirubin and alkaline phosphatase for the subjects who meet Hy's law criteria will be listed in a by-subject listing.

No analysis of urinalysis tests is planned for this study.

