⁶ Serum Chemistry includes Na, K, Cl, CO₂, Ca, P, BUN, creatinine, globulin, glucose, ALT, AST, LDH, alkaline phosphatase, total bilirubin, direct bilirubin, indirect bilirubin, total protein and albumin.
⁷ Females of childbearing potential only. Females who are either post-menopausal for at least 1 year or surgically sterile (documented by medical record) do not need to take pregnancy tests. In Austria only, at-home urine pregnancy testing will be completed at Week 15 and Week 21, as described in Section 7.5.6.
⁸ Urinalysis includes appearance, glucose, ketones, blood, protein, nitrite, bilirubin, specific gravity, pH, urobilinogen, and leucocyte esterase. If positive for blood or protein trace, microscopy will be included.
⁹ SAEs will be followed to resolution or stabilization unless the subject is lost to follow-up.
¹⁰ Haematology, serum chemistry and urinalysis only performed at Week 26 (Visit 10) if there are clinically significant abnormalities identified at Week 24 (Visit 9).
¹¹ Visit 9 renal biopsy should be collected within 14 days of Visit 9, and is not required to be collected during this visit itself; Visit 9 biopsy will not be required for subjects that withdraw early.

Table 3: Schedule of Study Procedures—Extended Treatment

Study Procedure	Every 12 weeks (± 2 weeks) until study results available	Dose Modification Visits Following transition of subject to 150 mg fostamatinib bid ¹
		2, 4, and 8 weeks from dose modification
Informed Consent	X ²	
Inclusion/Exclusion	X ²	
Blood Pressure	X	X
Haematology ³	X	X
Serum Chemistry ^{4,5}	X	X
Urine for Pregnancy ⁶	X	X
Urinalysis ^{5,7}	X	X
Urine for sPCR ⁵	X	X
Concomitant Medications	X	X
Adverse Event Evaluation ⁸	X	X
Study Drug Accountability	X	X
Dispense Study Drug ⁹	X	

¹ If a subject transitions to 150 mg fostamatinib *bid* during the extended treatment period as defined in [Section 7.11](#), visits will occur at 2, 4, and 8 weeks from the dose modification to confirm safety of the new treatment regimen. Starting 12 weeks after dose modification, the standard 12-week visit interval will resume.

² Prior to initiation of extended treatment, eligibility will be confirmed and eligible subjects will sign an informed consent addendum (see [Section 7.11](#)).

³ Haematology includes red blood cell count (RBC), white blood cell count (WBC), hemoglobin, hematocrit, WBC differential count (neutrophils, lymphocytes, eosinophils and basophils), MCHC, MCH, MCV, MPV, RDW, and platelet count.

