7.3 Study Follow-Up (Visit 10)

Subjects will be instructed to return to the clinic 2 weeks following the last dose of study drug for Follow-up Study assessments. Haematology, serum chemistry and/or urinalysis are to be performed only if there are clinically significant abnormalities identified in the corresponding panel at Week 24 (Visit 9). If an SAE is present at the last visit, follow-up should occur as indicated in [Section 9.2.1](#).

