10.4 Analysis of Safety

All safety variables will be analyzed using the Safety population. The safety population will include all randomised subjects who received at least 1 dose of the allocated study drug. The safety population will be used for analysis of all safety assessments through Visit 10. Safety data from the extended treatment period will not be included in the statistical analysis.

The safety endpoints will assess the safety and tolerability of fostamatinib as assessed by the incidence of adverse events, clinical laboratory results (haematology, serum chemistry, and urinalysis), vital signs, and physical examinations. Safety parameters of particular interest will include increases in blood pressure, adverse effects on liver function tests including transaminase elevations, diarrhoea, other GI symptoms and neutropenia.

The safety outcomes of this study include the change from baseline in blood pressure, liver function, and absolute neutrophil count (ANC) and the incidence of GI complaints and infections, as well as the incidence of any adverse events.

For each treatment group, descriptive statistics will be presented by visit for the actual values and the changes from baseline for systolic and diastolic blood pressure, each liver function test (ALT, AST, alkaline phosphatase, and bilirubin [total, direct, and indirect]), and ANC.

The difference between fostamatinib and placebo in the mean change from baseline will also be presented for each endpoint. The numbers and percentages of subjects with GI complaints and infections at any time during the double-blind treatment period will be presented by treatment group for the Safety Population. Fisher's Exact Test will be used to test for a difference between fostamatinib and placebo in the proportions of subjects experiencing GI complaints and infections.

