 - Tubulointerstitial scarring (interstitial fibrosis/tubular atrophy) score
- Frequency of AEs and SAEs by SOC and PT
- Change from baseline in eGFR (mL/min/1.73 m²) at Weeks 12 and 24
- Summary of ALT, AST and total bilirubin abnormalities based on maximum values
- Summary of ALT, AST, and serum creatinine by visit
- Summary of vital signs by visit

Only descriptive statistics for efficacy (and safety) data will be provided at the interim analysis. No inferential statistical analyses will be performed on the efficacy data. Additionally, no imputation will be done for missing data in the interim analysis; only observed data will be reported. Consequently, no adjustment for alpha spending will be made at the completion of the trial.

Listings of the data identified above will also be provided for the Cohort 1 subjects at the interim analysis.

9. Safety Review Committee

Because fostamatinib has been widely used in other treatment settings and its safety profile is well-known, no new safety issues were expected to be identified by this small study. However, because subjects are being treated in a new indication and at higher doses of fostamatinib than used in the large rheumatoid arthritis program from which the majority of prior safety information was collected, an unblinded Safety Review Committee (SRC) was established to periodically monitoring the emerging safety data from the trial. The composition, roles, and responsibilities of the SRC have been defined in a separate SRC charter document.

10. Visit Windows

Assessments will be reassigned to the scheduled visits according to the following visit windows. If there are multiple assessments assigned to the same visit window after the early termination visit reassignment, the non-missing value closest to the scheduled study day will be used. If there

are multiple assessments with non-missing values with the same number of days from the scheduled study day, the latest one will be used.

Table 5: Analysis Visit Window

Scheduled Visit	Study Day	Visit Window (Study Day)
Week 1	7	2 - 10
Week 2	14	11 - 21
Week 4	28	22 - 42
Week 8	56	43 - 70
Week 12	84	71 - 105
Week 18	126	106 - 147
Week 24	168	148 - 180
Week 26	182	181 or Later Not in Extended Treatment

11. Handling of Missing Data

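### Week 26 haematology and chemistry are drawn only after a clinically significant Week 24 abnormality, yet SAP 7.6.2 tabulates Week 26 as an ordinary visit, so that column is a selected subset, not comparable with earlier visits, and cannot show reversibility

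*SAP*

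**What the plan says.** **What is tabulated.** SAP 7.6.2 plans to summarise "Actual values and the change from baseline to each scheduled visit in hematology, serum chemistry" and quantitative urinalysis, by dose. Table 5 in SAP section 10 lists Week 26 (study day 182) among the scheduled visits, with the window "181 or Later Not in Extended Treatment". The protocol agrees. Its section 10.4 states that "The safety population will be used for analysis of all safety assessments through Visit 10", and for blood pressure, liver tests and neutrophil count that "descriptive statistics will be presented by visit for the actual values and the changes from baseline".

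**What is collected.** Protocol 7.3 (Visit 10) says "Haematology, serum chemistry and/or urinalysis are to be performed only if there are clinically significant abnormalities identified in the corresponding panel at Week 24". Footnote 10 to Protocol Table 2 gives the same condition, panels being "only performed at Week 26 (Visit 10) if there are clinically significant abnormalities identified at Week 24 (Visit 9"), and SAP Appendix A repeats that footnote.

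**What is missing.** Neither SAP 7.6.2 nor Protocol 10.4 excludes Week 26 laboratory values, confines them to listings, or labels them as a subset.

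**The concern.** If the plan is followed as written, each laboratory table has a run of columns for all attending subjects and a last column for subjects picked because of their Week 24 result. Two selections act on that column:

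- **Flagging.** A subject appears only if the panel was clinically significantly abnormal at Week 24. If the drug causes such abnormalities, the share flagged differs by arm, and a between-arm reading at Week 26 is no longer a comparison of randomised groups.
- **Extension.** Subjects in extended treatment are outside the Week 26 window. Under Protocol 7.11, entry requires a proteinuria or biopsy response and having tolerated study drug, so some of the better-tolerating subjects are left out.

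The stake is interpretive. Protocol 3.5 describes the neutrophil and liver-test effects as reversible, and 3.5.3 gives a typical 5 to 7 days for neutropenia to resolve after stopping. Visit 10, two weeks after the last dose, is the only scheduled off-drug laboratory point in the main study. A reader will look there for reversibility, on parameters that the protocol names as of particular interest.

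**Working it through.** The plan gives no figure for this point, so there is none to reproduce. The check asks which way the selection pushes the planned columns.

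**Inputs from the documents:** the sampling rule, the by-visit summary and the Week 26 window set out above; 25 subjects per group (Table 1); eligibility limits on ANC, haemoglobin, ALT/AST and bilirubin at Visit 1b (exclusion criterion 6).

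**Assumptions, not in the documents:** share flagged q = 10–20%; normal values in baseline SD units, higher = worse; within-subject correlation ρ = 0.3–0.7; drug shift μ = 0 or 0.5 SD, with between-subject SD σ = 0 or 0.5; fraction of the effect persisting off drug p = 1, 0.5 or 0. The tabulated analyte is taken to be the one that triggered the re-test.

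**Model.** Y0 = a + e0; Y24 = a + b + e24; Y26 = a + p·b + e26, with Var(a) = ρ, Var(e) = 1 − ρ and b having mean μ and SD σ. Y26 is seen only if Y24 lies in the worst fraction q of its arm. With k = φ(z)/q and S = √(1 + σ²):

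- mean Y26 in the selected = p·μ + k·(ρ + p·σ²)/S
- mean Y0 in the selected = k·ρ/S
- k = 1.40 for q = 20%; k = φ(1.2816)/0.10 = 1.755 for q = 10%

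**Worked cases.** No effect, q = 20%, ρ = 0.5: Week 26 mean = 1.40 × 0.5 = 0.70; baseline mean of the same subjects = 0.70; change = 0.00. Half-reversed effect, σ = 0.5, so S = √1.25 = 1.118: Week 26 mean = 0.25 + 1.40 × 0.625/1.118 = 1.03; baseline mean = 1.40 × 0.5/1.118 = 0.63; change = 0.41 (unrounded terms).

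**Planned columns: Week 24 (all) → Week 26 (selected).** Simulation with 2,000,000 subjects per scenario gave:

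| Scenario | Actual value | Change from baseline | True all-subject Week 26 change |
|---|---|---|---|
| No effect, q 20%, ρ 0.5 | 0.00 → 0.70 | 0.00 → 0.00 | 0.00 |
| No effect, q 10%, ρ 0.7 | 0.00 → 1.23 | 0.00 → 0.00 | 0.00 |
| No effect, q 10%, ρ 0.3 | 0.00 → 0.53 | 0.00 → 0.00 | 0.00 |
| No effect, q 20%, ρ 0.5, Week 24 and 26 errors correlated 0.3 | 0.00 → 0.91 | 0.00 → 0.21 | 0.00 |
| No effect, q 20%, ρ 0.5, baseline truncated at 1.5 SD (stand-in for eligibility) | −0.07 → 0.55 | 0.07 → 0.17 | 0.07 |
| Effect 0.5, same in all, no reversal* | 0.50 → 1.20 | 0.50 → 0.50 | 0.50 |
| Effect 0.5, σ 0.5, no reversal* | 0.50 → 1.44 | 0.50 → 0.81 | 0.50 |
| Effect 0.5, σ 0.5, half reversed* | 0.50 → 1.03 | 0.50 → 0.41 | 0.25 |
| Effect 0.5, σ 0.5, fully reversed* | 0.50 → 0.63 | 0.50 → 0.00 | 0.00 |

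*q 20%, ρ 0.5.

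Actual values look worse at Week 26 in every row, even when the effect has fully reversed. Change from baseline equals the truth in some rows and is too high in others, and nothing in the table tells the reader which case applies.

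**Numbers and arms.** At 10–20% flagged, a group of 25 leaves about 2.5 to 5 subjects at Week 26. If a common threshold flags 20% of placebo (z = 0.842), a 0.5 SD drug shift raises the flagged share to 1 − Φ(0.842 − 0.5) ≈ 37%, about 9 of 25 against 5 of 25.

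**Paired comparison, not planned.** Following only the flagged subjects with no drug effect (q 20%, ρ 0.5), the mean value falls from 1.40 to 0.70 and the mean change from 0.70 to 0.00. That is pure regression to the mean.

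**The case against.** A reader might infer that regression to the mean will make the Week 26 column show a false recovery. The documents do not support that. SAP 7.6.2 sets all subjects at Week 24 beside selected subjects at Week 26, and a group chosen for being abnormal looks worse than the whole arm. False recovery needs a Week 24 mean for the flagged subjects alone, which 7.6.2 does not plan. The same fact limits the remedy: a table counting flagged subjects who return to normal would bring in the very bias that the planned column lacks.

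Other points in the plan's favour:

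- **The selection is partly visible.** SAP section 7 reports the number of non-missing observations, so a small Week 26 n would show, and SAP Appendix A carries the sampling footnote. This lessens the harm. It does not make the column comparable, nor put the warning on the table.
- **Listings already exist.** SAP section 7 lists all collected data by subject. That stands, and it makes the fix cheaper.
- **Selection is diluted.** A whole panel is repeated, so an analyte that did not trigger the re-test is selected only through its correlation with the trigger. That stands; the trigger-analyte figures are towards the upper end for the assumed flag rates and correlations.
- **Reversibility is background.** It is neither an objective nor an endpoint, laboratory safety is descriptive, and no sPCR is scheduled at Visit 10, so the primary analysis is untouched. All of this stands and sets the severity.

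**Conclusion.** The concern holds in this form: the Week 26 haematology and chemistry column is conditioned on the Week 24 outcome, its make-up can differ by arm, and the plan treats it as an ordinary visit. It is not comparable with earlier columns. Actual values will tend to look worse than at Week 24: by 0.53–1.23 SD with no drug effect in the equal-correlation cases, for the trigger analyte. Change from baseline ranges from unbiased to overstated (0.81 against a true 0.50, or 0.41 against a true 0.25), so real recovery may be understated. The column cannot establish reversibility either way.

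The direction for actual values follows from the selection rule. The sizes rest on assumed flag rates, correlations, normality and effect patterns that the documents do not give, and they shrink for analytes that did not trigger the re-test. Severity is minor to moderate.

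**What to change.** In SAP 7.6.2, add wording to this effect:

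> Week 26 haematology and chemistry results are excluded from the by-visit summaries and from any by-visit shift table, because they are collected only after a clinically significant abnormality in that panel at Week 24. They will be presented in a by-subject listing (baseline, Week 24, Week 26), with the number of subjects flagged at Week 24 and the number re-tested, per treatment group.

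If a count of values returning to normal is also shown, footnote the table with the selection rule and state that normalisation includes regression to the mean and is not evidence of reversibility.

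SAP 7.6.2 does not say whether its shift tables are by visit; that should be made explicit. For urinalysis, 7.6.2 first plans summaries and then says that none is planned. Reconcile those sentences before deciding how Week 26 urinalysis is handled.

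The cost is SAP wording and one listing with counts, with no new data. The downside is losing the Week 26 summary column.

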3.5.2 Liver Function Test Abnormalities

Mild to moderate increases in liver enzymes (ALT and AST) have been observed in fostamatinib-treated patients. A very small number of patients have experienced elevations $> 10 \times$ ULN. LFT abnormalities can occur at any time during the course of treatment. Mild increases in total and indirect bilirubin have also been observed in some fostamatinib treated patients and it has been determined that R406, the primary metabolite of fostamatinib, inhibits the enzyme UGT1A1 at fairly low concentrations (500 nM, concentrations regularly achieved clinically). While this effect is clinically innocuous, it requires consideration when interpreting liver function test results.

A total of 5 patients across the fostamatinib program have met the criteria for potential drug-induced liver injury but have not met the formal Hy's law criteria. Two patients had alternative explanations for the abnormalities, one did not have simultaneous elevation of bilirubin and transaminases, and two patients had the UGT1A1*28 polymorphism upon genotyping.

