Appendix 1: Guideline for Dose Modification for Possible Drug-Induced Liver Injury (DILI): AST or ALT 3x ULN or TBL > 2xULN

The Investigator is responsible for determining whether the subject meets Hy’s law criteria for severe liver injury: aspartate aminotransferase (AST) or alanine aminotransferase (ALT) \geq 3x upper limit of normal (ULN) plus total bilirubin (TBL) > 2x ULN and alkaline phosphatase (ALP) < 2x ULN.

- **Note:** Fostamatinib is an inhibitor of UGT1A1, the enzyme responsible for the glucuronidation of bilirubin; occasionally an isolated increase in total and unconjugated (indirect) bilirubin may be observed. Study drug should not be held for an isolated increase in total and unconjugated (indirect) bilirubin.
- The study Medical Monitor should be notified immediately of any potential case meeting Hy’s law criteria.

Table 1: Dose Adjustment

Starting Dose	Dose Level -1	Dose Level -2	Dose Level -3 ^a	Dose Level -4 ^a
100 mg PO bid	150 mg PO qd	100 mg PO qd	Discontinue	-----
150 mg PO bid	100 mg PO bid	150 mg PO qd	100 mg PO qd	Discontinue

^a The Sponsor’s Medical Monitor should be consulted prior to consideration of dose modification to levels -3 or -4.

Identification

If AST or ALT \geq 3x ULN and total (and/or conjugated) bilirubin > 2x ULN, with ALP < 2x ULN (Hy’s law criteria met), the Investigator should follow the instructions below:

- Stop study drug treatment immediately and withdraw the subject from the study for possible drug-induced liver injury.
- Complete the appropriate LFT module of the case report form (CRF) with the original laboratory test results.
- Follow the subject until liver biochemistry parameters and any clinical symptoms and signs return to normal or baseline levels, or as long as medically indicated.
- Investigate the etiology of the event and perform diagnostic investigations as discussed with the Sponsor’s Medical Monitor.

If AST or ALT \geq 3x ULN or total (and/or conjugated) bilirubin > 2x ULN, and the subjects are exhibiting the following symptoms: nausea, vomiting, abdominal pain:

- Withhold/ interrupt dosing with study drug immediately.
- Repeat LFTs, including bilirubin and alkaline phosphatase every 3 days/72 hours until ALT/AST or total (and/or conjugated) bilirubin returns to < 1.5x ULN.

- Complete the appropriate LFT module of the CRF with the original laboratory test result.

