3.1 General Description

This is a Phase 2, multi-center, randomized, double-blind, ascending-dose, placebo-controlled, proof-of-concept study to evaluate 2 dose regimens of fostamatinib in approximately 75 subjects. The study will consist of 11 visits over 28 to 43 weeks.

The study consists of 3 phases: a screening phase, a double-blinded treatment phase and a follow-up phase. Figure 1 presents the study design.

Figure 1: Study Design

Subjects who meet all inclusion/no exclusion criteria will be required to have completed at least 90 days of treatment with either an angiotensin converting enzyme inhibitor (ACEi) or angiotensin II receptor blocker (ARB) at the maximum approved (or tolerated) dose, and to have had a pre-study renal biopsy no more than 180 days prior to randomization (more than 180 days may be approved by the medical monitor on an individual basis). The renal biopsy will be reviewed by a member of the central panel of renal pathologists to ensure subjects meet histological entry criteria (complete scoring by the full panel will occur following randomization).

The enrollment plan for this study is to randomize patients in an ascending dose fashion. Once randomization of the initial cohort of 38 subjects (approximately 25 randomized to fostamatinib 100 mg bid, 13 to placebo) is complete, screening may begin for the second cohort of approximately 37 subjects (approximately 25 randomized to fostamatinib 150 mg bid, 12 to placebo). All subjects in Cohort 2 (150 mg bid or placebo) will be required to have proteinuria >1 gm/day (USA only) or > 0.5 gm/day (rest of the world) at Screening Visit 1b. Subjects will be randomized 2:1 in each cohort to maintain 1:1:1 allocation for all 3 double-blind dosing groups (25 subjects per group: see Table 1). Randomization will be stratified among the 3 treatment groups by presence or absence of endocapillary hypercellularity, as determined by a member of the central panel of renal pathologists on the most recent pre-study renal biopsy obtained prior to randomization (see Figure 1).

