5.5 Treatment Groups for Analysis

For descriptive summaries, the following treatment groups will be used, unless otherwise indicated.

- Placebo (all placebo groups)
- 100 mg bid fostamatinib group
- 150 mg bid fostamatinib group
- Combined fostamatinib group

For comparisons of treatment differences in the analyses of efficacy endpoints, estimates of the following contrasts will be provided, unless otherwise indicated:

- Combined fostamatinib group vs placebo
- 150 mg bid fostamatinib group vs placebo
- 100 mg bid fostamatinib group vs placebo

For all the by-subject listings, the randomized treatment group will be presented.

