R_i = total number of tablets returned for visit interval i

$T_i = 2$ for bid dosing and $=1$ for qd dosing, for visit interval i

P_i = total number of days in visit interval i .

The total number of tablets that were supposed to be taken during the double-blind treatment period excludes the number of tablets not taken due to a dose interruption. If a patient fails to return a study drug kit dispensed during the double-blind treatment period, then study drug compliance is considered to be missing.

Baseline sPCR: Two baseline sPCR value will be used in the analysis. In primary efficacy analysis, the baseline sPCR is defined as the average of non-missing value between Visit 2 and the most recent screening value prior to Visit 2. If only one non-missing sPCR is available, this value will be used as baseline.

A **Treatment-Emergent Adverse Event (TEAE)** is any adverse event that emerges on or after first dosing and prior to the end of follow-up (having been absent prior to treatment) or worsens relative to the pre-treatment state.

Hy's Law criteria are: concurrent aspartate aminotransferase (AST) or alanine aminotransferase (ALT) $\geq 3x$ upper limit of normal (ULN) with total (and/or direct/conjugated) bilirubin (TBL) $> 2x$ ULN and alkaline phosphatase (ALP) $< 2x$ ULN, and no other reason can be found to explain the combination of increased aminotransferase and serum total bilirubin, such as viral hepatitis, alcohol abuse, ischemia, preexisting liver disease, or another drug capable of causing the observed injury.

Prior Medications will be defined as the medications used prior to the first dose of study drug. If the medication is used both prior to and on/after the first dose of study drug, the medication is both prior medication and concomitant medication.

Concomitant Medication will be defined as the medications used on/after the first dose of study drug.

7. Statistical Methods

The statistical analysis of the data obtained from this study will be performed using SAS® version 9.4 or higher. All inferential tests will be 2-sided and will be performed using a type I error rate of 5%, unless otherwise indicated.

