7.2 Demographics and Baseline Characteristics

Demographics and baseline characteristics will be summarized by treatment in the ITT population.

Medical history will be coded using the Medical Dictionary for Regulatory Affairs (MedDRA), using the latest version available at the time of the interim analysis, as specified in the Data Management Plan (DMP). The medical history conditions will be summarized by treatment, system organ class and preferred term in the ITT population.

Prior IgA Nephropathy and Concomitant medications will be coded using the latest version of the World Health Organization Drug Dictionary (WHO-DDE) available at the time of the IA, as specified in the DMP. Prior and concomitant medications will be summarized by treatment,

anatomical therapeutic chemical classification (ATC) level 2 term and preferred term in the ITT population. Additionally, the number and percentage of Subjects who changed anti-hypertensive regimen during the treatment period, either in medication or dose of medication, will be summarized by study stage and listed. Anti-hypertensive medications are medications with the following ATC codes:

- CO2: Anti-hypertensives
- CO3: Diuretics
- CO4 Peripheral Vasodilators
- CO7: Beta blocking agents
- CO9: Agents acting on the renin-angiotensin system.

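### SAP 7.6.2 groups the table of raised transaminases and Hy's law cases by an undefined study stage, and the SAP's Hy's law definition can leave out subjects who meet the protocol's laboratory criteria

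*SAP*

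**What the plan says.** SAP 7.6.2 (Clinical Laboratory Evaluations) plans the number and percentage of subjects with elevated transaminase tests or meeting Hy's law after the first dose: "defined as the assessments after the first dose of study drug) will be summarized by study stage". It adds a by-subject listing of liver tests, limited to subjects who meet Hy's law.

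The only other use of study stage is in SAP 7.2, for changes in anti-hypertensive regimen: "will be summarized by study stage and listed". Neither place defines it. The nearest defined idea is in SAP 3.1: "The study consists of 3 phases: a screening phase, a double-blinded treatment phase and a follow-up phase".

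SAP 5.5 sets a default: "For descriptive summaries, the following treatment groups will be used, unless otherwise indicated". The groups that follow are placebo, 100 mg, 150 mg and combined fostamatinib.

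On Hy's law, SAP Section 6 (Analytic Definitions) gives laboratory limits and then a further condition: "and no other reason can be found to explain the combination of increased aminotransferase and serum total bilirubin". Protocol Appendix 1 gives the laboratory limits only, AST or ALT at least 3x "upper limit of normal (ULN) plus total bilirubin (TBL) > 2x ULN and alkaline phosphatase (ALP) < 2x ULN".

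For the Cohort 1 interim, SAP Section 8 lists among its by-treatment-group outputs: "Summary of ALT, AST and total bilirubin abnormalities based on maximum values".

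**The concern.** Liver test abnormality is a safety parameter of interest in both documents (protocol 4.4, SAP 4.4), and protocol 3.5 describes it as dose-dependent. The table that should show how many subjects in each arm had a marked elevation is given a grouping that is undefined and does not mention arm. A programmer who follows the sentence literally would produce one pooled column per stage.

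The Hy's law count in the same table follows a stricter rule than the protocol's own. Under Appendix 1 a subject who reaches the laboratory limits meets Hy's law and is withdrawn. Under SAP Section 6 that subject can be counted as not meeting it. Because the dedicated listing uses the same criterion, the subject would not appear there either. At stake is whether a reader of the final report can see, by arm, the few liver findings that matter most.

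**Working it through.** The plan states no figure to reproduce here, so the check is mainly a comparison of texts.

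**1. Grouping.** Neighbouring safety outputs name the arm or dose: chemistry values by dose (SAP 7.6.2), vital signs by dose and visit (7.6.3), treatment-emergent events by treatment (7.6.1). The liver count names study stage instead. If that means the SAP 3.1 phases, data after the first dose can fall only under treatment or follow-up. The follow-up column would also be selective, because Week 26 chemistry is drawn only after a clinically significant abnormality at Week 24 (protocol 7.3).

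**2. Cut-offs.** SAP 7.6.2 gives no ULN multiple for an elevated transaminase. Other parts of the documents do use multiples: 3x and 5x ULN in Appendix 1, and above 10x ULN in protocol 3.5.2.

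**3. Hy's law.**

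| | Protocol Appendix 1 | SAP Section 6 |
|---|---|---|
| AST or ALT | at least 3x ULN | at least 3x ULN |
| Bilirubin | above 2x ULN | above 2x ULN |
| ALP | below 2x ULN | below 2x ULN |
| Other cause excluded | not required | required |
| Who decides on other cause | not applicable | not stated |
| Blinding of that decision | not applicable | not stated |

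Consider a subject who meets all three limits and for whom another drug is named as a possible cause. Appendix 1 treats the criteria as met. SAP Section 6 does not, so the subject is absent from the Hy's law count and its listing. The subject would remain in the raised-transaminase count and in the general listings, but not marked as a case.

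**4. Other final liver outputs.**

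| Output | Arms kept apart? | Limitation |
|---|---|---|
| Chemistry values and changes (SAP 7.6.2) | by dose | averages dilute a few large elevations |
| Shift tables (SAP 7.6.2) | grouping not stated | only low/normal/high, so just above ULN and above 10x ULN share a category |
| Events of special interest, including ALT, AST and bilirubin increases (SAP 7.6.1) | by treatment | depends on adverse event reporting |
| General by-subject listings (SAP 5.5 and 7) | randomised group shown | no counts |
| Interim maximum-value abnormalities (SAP 8) | by treatment group | Cohort 1 only; no explicit final counterpart |

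**5. Illustration of literal pooling (assumed counts, planned arm sizes).** With 3x ULN reached in 4/25 = 16% (150 mg), 1/25 = 4% (100 mg) and 0/25 = 0% (placebo), a pooled column shows (4 + 1 + 0)/75 = 5/75 = 6.7%.

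**6. What counts of this size can show.** If no case occurs, the one-sided 95% upper bound is 1 − 0.05^(1/n). This gives 5.8% for n = 50 on fostamatinib and 11.3% for n = 25 on placebo. With 0/25 on placebo, Fisher's exact test (two-sided) gives p = 0.088 for 7/50 on fostamatinib and p = 0.046 for 8/50. SAP 7.6 plans no safety tests, so this is only a gauge. Hy's law counts will be very sparse under either definition, and the by-arm count of transaminase elevations carries more information.

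**The case against.** The strongest reply is that SAP 5.5 already makes the treatment groups the default for descriptive summaries, so study stage may be an extra breakdown within those columns. That is a fair reading, and pooling is not proven. But the default yields where something else is indicated, and naming another grouping is arguably such an indication. The ambiguity stands.

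A second reply is that the final report will still show liver data by arm. This is correct. A reader might infer that the plan cannot show any drug-placebo difference in liver safety; the outputs in the second table above rule that out. Nor is this the only threshold-based liver table, since the shift tables use LLN and ULN. The final analysis is also not weaker than the interim overall: it adds the 150 mg arm, and only the maximum-value table lacks an explicit final counterpart.

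Third, the no-other-cause condition affects only the Hy's law count, applies in every arm and does not by itself prevent a comparison. That stands too. Appendix 1 also governs patient management rather than tabulation. Even so, using one label for two definitions lets the report contradict the withdrawal record.

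Fourth, the programme history is thin support. Protocol 3.5.2 reports: "A total of 5 patients across the fostamatinib program have met the criteria for potential drug-induced liver injury". A reader might infer that a causality rule removed all five. The text attributes only two to alternative explanations; one lacked simultaneous elevation and two had a UGT1A1 polymorphism. Set roughly against the more than 3,000 patient-years in rheumatoid arthritis (protocol 3.1), five cases imply about 5/3,000 × (50 × 24/52) = 0.04 expected among 50 fostamatinib subjects. The Hy's law count may well be zero under either definition.

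**Conclusion.** The point holds for one table and one listing. Three facts are clear from the text: study stage is undefined, no ULN multiple or treatment group is named for the liver count, and the SAP's Hy's law rule is narrower than the protocol's. That arms would actually be pooled is a literal reading held with moderate confidence, because the SAP 5.5 default may have been intended. That a laboratory-defined case can drop out of the count and listing follows directly from the two definitions, though such a case may never occur in a trial of about 75 subjects.

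No size can be derived from the documents. The 6.7% against 16%, 4% and 0% comparison rests on assumed counts and on the pooled reading. The matter should still be corrected before the final analysis, because following the plan as written can hide by-arm liver findings and the repair is small.

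**What to change.** In SAP 7.6.2:

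- Replace the study-stage grouping with the SAP 5.5 groups (placebo, 100 mg, 150 mg, combined fostamatinib). Define or delete the same term in SAP 7.2.
- Tabulate maximum post-baseline ALT or AST at stated multiples of ULN, bilirubin above 2x ULN, and the Appendix 1 laboratory combination regardless of cause.
- List every subject who meets the laboratory combination. Show alternative cause as a separate assessment column, and state who makes that assessment and that it is made blind to treatment.

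In SAP Section 6, remove the no-other-cause condition from the counting rule and keep it as the definition of that assessment. The change concerns tabulation only and leaves the clinical rules in Appendix 1 untouched.

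The cost is a few lines of SAP text, one re-specified table and one extended listing. The laboratory data are already collected; only the cause assessment might need a short review of any case that arises.
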